### 9.3. Adverse Events of Special Interest

AESIs are defined as events known as related to treatment with DPP1 inhibitors and will be identified through the AE form by looking into the "AESI Category" selected by the investigator. Additional information on AESIs will be collected on dedicated eCRF forms. Tabulations will be prepared for each event type by treatment group:

- Hyperkeratosis,
  - Hyperkeratosis events by severity and signs. Tabulation will be separated to include investigator and dermatologist assessments
  - Hyperkeratosis events by SOC and PT
- Severe Infection
  - by MedDRA SOC and PT
  - Infection-Pneumonia events
  - Severe infections by SOC and PT
- Periodontitis/Gingivitis,
  - the median time from randomization to first referral of a participant.
     Censoring will not be applied
  - distribution of changes in Patients Pocket Depth (PPD) from first to follow-up periodontitis assessment
  - participants with number of change >=2 and size change >=2 mm in PPD from first to follow-up periodontitis assessment
  - participants with 2 sites of a change >= 2 mm and the number of changes >= 2 mm in PPD

CONFIDENTIAL Page 76 of 139

- dental TEAEs
- distribution of gingival inflammation
- Severe periodontitis/gingivitis events by SOC and PT

A summary of the incidence will be provided for each TEAESI by treatment group. In addition, the risk difference estimate (unadjusted) and the exact 95% confidence interval will be provided for treatment comparison between each brensocatib dose and placebo.

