## 9.10.3. Adverse Event of Special Interest

AESIs are defined as events known as related to treatment with DPP1 inhibitors. Additional information on AESIs will be collected in the eCRF. The AESI category groups and preferred terms include the following: hyperkeratosis, infection, and periodontal/gingival events.

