# 9.10.3.2. Periodontitis/Gingivitis

Adult subjects will be advised to conduct self-monitoring of their oral soft tissue, gingiva, and tooth mobility, and report any findings. For adolescents, oral and dental inspection for any signs or symptoms of gingivitis or periodontitis will be performed by the Investigator at each visit.

Occurrence of periodontitis during the study will be considered an AESI. If there are any signs or symptoms of periodontitis or gingivitis that warrant further evaluation upon Investigator discretion, the subject will be referred to a dentist/periodontist for further assessment and treatment. Subjects will be discontinued from the trial if they develop severe periodontal disease as defined by:

- Pocket depth measurement and attachment loss ≥6 mm on 2 or more teeth
- Have Class 3 mobility or Class 3 furcation involvement

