#### 9.10.3.3. Other Infections

Subjects will be monitored throughout the study for potential infections. Any severe infection, defined as any infection requiring treatment with parenteral antibiotics/antiviral/antifungal agent, any clinical endoparasitosis, and any opportunistic infection should be considered as AESI. Generally, all uncommon, atypical, or unusually persistent infections should be reported as AESIs.

Note: Pulmonary exacerbations do not fall into this AESI category. Protocol-defined PEs are collected as efficacy endpoints (Section 9.10.1).

Pneumonia will be a specific subcategory within the other infections AESI and will be monitored through the study.

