### 9.4. M8 (Thiocyanate) Toxicity Analysis

To evaluate the impact of brensocatib treatment on AEs that might have potential association with M8 (thiocyanate), including hypothyroidism, hypotension, and neurotoxicity, additional investigations will be made.

The thiocyanate-related AEs will be identified using a hierarchical approach such that MedDRA FDA Medical Queries (FMQs) will be used when available and MedDRA Standardized Medical Queries (SMQs) will be used when an FMQ is unavailable. When an FMQ and SMQ are both unavailable, a Customized Medical Query (CMQ) will be created.

The following thiocyanate-related AEs will be identified.

- FMQs:
  - Hypotension (FMQ grouping: hypotension)
  - Seizures (FMQ grouping: Seizure)
  - Confusion (FMQ grouping: Confusional State)
- SMQs:
  - hypothyroidism (SMQ narrow category: hypothyroidism)
  - delirium (SMQ narrow category: noninfectious encephalopathy/delirium)
- CMO:
  - Hallucinations
    - (Preferred Terms):
      - Hallucination aggravated
      - Kinesthetic hallucination
      - Organic hallucinosis syndrome
      - Hallucinations
      - Hallucination NOS
      - Sensory hallucinations
      - Drug-induced hallucinosis
      - Hallucinating
      - Stump hallucination

For hypotension, blood pressure will also be investigated for abnormalities defined as:

- Systolic blood pressure <90 mmhg and diastolic blood pressure <60 mmhg, or
- Change from Baseline in systolic and diastolic blood pressure >=30 mmHg,

The number and percentage of participants with an AEs that might have potential association with M8will be presented in an overview table. The M8 concentrations in plasma, when

CONFIDENTIAL Page 77 of 139

available, will be described descriptively and changes from baseline until the time point the AE reported the very first time.

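### AESI incidence and risk differences rest only on the category the investigator selects, and pocket depth is tabulated only as change, so depth present at the first dental assessment does not show in those tables

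*SAP*

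**What the plan says.** Protocol 9.10.3 names the groups: "The AESI category groups and preferred terms include the following: hyperkeratosis, infection, and periodontal/gingival events". It refers to preferred terms but lists none. The following subsections define the events by content:

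- **Periodontal (9.10.3.2):** "Occurrence of periodontitis during the study will be considered an AESI".
- **Infection (9.10.3.3):** a severe infection, "defined as any infection requiring treatment with parenteral antibiotics/antiviral/antifungal agent". Endoparasitosis, opportunistic infections and unusual or persistent infections are added. Pulmonary exacerbations (PEs) are excluded.

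SAP 9.3 identifies the events differently: "AESIs are defined as events known as related to treatment with DPP1 inhibitors and will be identified through the AE form by looking into" the category field completed by the investigator. Each TEAESI then gets an incidence by arm and an unadjusted risk difference against placebo with an exact 95% interval.

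For periodontal findings, SAP 9.3 plans the "distribution of changes in Patients Pocket Depth (PPD) from first to follow-up periodontitis assessment". Two further pocket-depth items count changes of at least 2 mm. It also lists time to first referral, dental TEAEs, gingival inflammation and severe periodontitis/gingivitis events. The protocol's definition of severe periodontal disease is an absolute level: "Pocket depth measurement and attachment loss" of at least 6 mm on two or more teeth, with Class 3 mobility or furcation as a second item.

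**The concern.** Hyperkeratosis, periodontal events and infections are the risks the protocol expects from DPP1 inhibition (Protocol 1.4.2). They are also the adverse events for which SAP 9.3 plans risk differences with intervals. Those comparisons depend on one field being completed correctly at over 400 sites, and the plan has no step to find qualifying events that were left uncategorised. Elsewhere the SAP does use terms: preferred terms for COVID-19, COPD and asthma (Appendix K), and standard queries for M8-related events, where if none exists "a Customized Medical Query (CMQ) will be created" (SAP 9.4).

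The pocket-depth tables have a separate limit. They describe what happened after the first dental assessment, and in this trial that assessment follows a referral. They cannot show how deep the pockets were when first measured.

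**Working it through.** The plan states no figure that can be reproduced here. The check is a comparison of the texts, followed by an illustration.

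**1. Following an uncategorised event.** Take a TEAE coded to Periodontitis with no AESI category selected. It qualifies under Protocol 9.10.3.2.

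| Planned output | Includes it? |
|---|---|
| TEAEs by SOC and PT, by PT, by maximum severity (SAP 9.2) | Yes |
| TEAESI row of the overview; listing triggered by a TEAESI (SAP 9.2) | No, unless another TEAESI (or, for the listing, a serious TEAE or IP withdrawal) brings the participant in |
| TEAESI incidence and risk difference (SAP 9.3) | No |
| Adolescent AESI subgroup (SAP 9.6) | No |
| Dental TEAEs (SAP 9.3) | Unclear; no identification rule is given |

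An infection AE treated parenterally follows the same path. Appendix K contains no AESI codes.

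**2. Effect on the risk difference (illustration).** Let p1 and p0 be the true risks, and s1 and s0 the shares of qualifying events categorised. The expected observed difference is s1·p1 − s0·p0, which is s(p1 − p0) when the shares are equal.

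Arm sizes are 540 + 16 = 556 for a brensocatib dose and 540 + 8 = 548 for placebo (planned adults plus adolescents). The risks and shares are assumptions. The chance that a 95% interval excludes zero is approximately Φ(RD/SE − 1.96), with SE = √(p1(1−p1)/556 + p0(1−p0)/548) at the observed risks.

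| Share categorised | Observed risks | RD (points) | SE | Chance |
|---|---|---|---|---|
| 100% | 10% v 5% | 5.0 | 0.01577 | Φ(3.17 − 1.96) = 0.887 |
| 70% | 7% v 3.5% | 3.5 | 0.01337 | Φ(2.62 − 1.96) = 0.745 |
| 50% | 5% v 2.5% | 2.5 | 0.01140 | Φ(2.19 − 1.96) = 0.592 |

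At lower assumed risks, with 540 per arm and a pooled variance in the test:

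| True risks | RD at 100 / 80 / 50% | Chance at 100 / 80 / 50% |
|---|---|---|
| 5% v 2% | 3.0 / 2.4 / 1.5 | 0.766 / 0.667 / 0.468 |
| 3% v 1% | 2.0 / 1.6 / 1.0 | 0.651 / 0.554 / 0.379 |

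Shrinkage is not guaranteed if the shares differ by arm. With 10% v 5%, shares of 70% and 90% give 7 − 4.5 = 2.5 points; reversed, they give 9 − 3.5 = 5.5 points.

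**3. Pocket depth.** Protocol Table 5 (footnote y) schedules questions about periodontal complaints, plus an investigator inspection in adolescents. No pocket measurement is scheduled. A dentist or periodontist is involved on referral, for assessment and treatment (Protocol 9.10.3.2). The SAP says only first assessment; that this means the referral visit is an inference from the absence of any scheduled examination. By contrast, the Phase 2 study had dental assessments at Baseline and Weeks 8 and 24 (Protocol 1.2.2.3).

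It follows that:

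- pockets of 7 mm at both the first and follow-up assessments give a change of 7 − 7 = 0;
- a reduction after dental treatment is recorded as improvement;
- one assessment gives no change at all.

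No SAP table gives absolute depth or applies the 9.10.3.2 criterion.

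**The case against.** The strongest reply is that selecting the category is how the protocol definition is meant to be applied. Protocol 9.10.3.3 tells investigators what to report as an AESI, and part of it (uncommon, atypical or unusually persistent infections) is clinical judgement that no term list can reproduce. AESIs also have dedicated eCRF forms, and data checks outside these documents may reconcile the field. All this stands. It is a reason to keep the category-based count, but not to leave it without a cross-check.

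Three stronger readings are tempting, and the documents do not support them:

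- **That uncategorised events are counted nowhere.** They remain in the general TEAE tables, and SAP 9 promises listings for its summaries. Those tables, however, scatter skin and infection terms, do not use parenteral treatment to identify events, and carry no planned risk difference.
- **That severe periodontal cases are invisible.** Protocol 9.10.3.2 says subjects meeting the criterion will be discontinued from the trial, so they should appear among the discontinuations (SAP 7.1) and possibly among TEAEs leading to withdrawal. Protocol 4.2.2.1 says only that study drug may be stopped. Even if the mandatory wording is followed, withdrawals are not a count of cases by arm. Also, a 7 mm pocket alone does not meet the criterion, which includes attachment loss.
- **That the AESI comparison is shown to be biased.** Nothing in the documents shows under-reporting of the category.

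A parenteral-drug rule has its own hazard. Severe PEs are defined by IV antibacterial treatment and/or hospitalization (Protocol 7.1), so a careless link would pick up mainly those.

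**Conclusion.** The point holds as a gap in verification. The TEAESI incidence and risk differences have no term- or criterion-based check on the investigator's category, so a qualifying but uncategorised event drops out of them. The pocket-depth tables, being changes only, cannot show depth present at the first assessment or any participant assessed once.

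The size is unknown. Proportional shrinkage of the risk difference requires equal capture in each arm. The chances above rest on invented risks and shares, use a normal approximation (the planned exact intervals would be somewhat wider), and concern a comparison outside the 12 tested hypotheses. No efficacy conclusion is affected.

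Absolute depth would not settle causation either. Exclusion criterion 25 removes diagnosed periodontal disease only if it is under treatment or procedures are expected, so disease present at entry cannot be separated from on-study disease within a participant. The between-arm comparison is what would be informative.

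**What to change.** Before unblinding, amend SAP 9.3 as follows.

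1. Fix a preferred-term list for hyperkeratosis and for periodontal/gingival events. For infections, define a rule: an infection AE linked to a parenteral antibiotic, antiviral or antifungal, excluding PEs, including reported ones that fail adjudication.
2. Present TEAESI incidence, risk difference and exact interval for events identified by category **or** by term/criterion, beside the category-only result.
3. Add by arm the distribution of pocket depth at the first assessment and the maximum at any assessment, with the number assessed. As far as the eCRF captures the components (pocket depth and attachment loss, mobility, furcation), add the number and percent meeting the Protocol 9.10.3.2 criterion as written.
4. State how dental TEAEs are identified.

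Separately, Protocol 4.2.2.1 and 9.10.3.2 must be reconciled on discontinuation when the periodontal criteria are met.

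The cost is a term list, a medication link (Appendix K already uses route of administration) and a few table rows. The planned analysis is unchanged. The drawback is that some added events will be atypical or pre-existing, and the category-only column lets the reader judge their effect. Participants never referred would count as not meeting the criterion, which is why the number assessed must be shown.

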#### 3. STUDY DESIGN

## 3.1. Summary of Study Design

This is a Phase 3, randomized, double-blind, placebo-controlled, parallel-group, multicenter, multinational study to assess the efficacy, safety, and tolerability of 2 doses of brensocatib compared with placebo in participants with NCFBE. Approximately 1,620 adult participants will be randomized in a 1:1:1 ratio to 3 treatment arms (540 participants per treatment arm) to receive brensocatib 10 mg QD, brensocatib 25 mg QD, or matching placebo QD for 52 weeks (refer to Section 3.3). For this study, the adolescent population is defined as participants ≥12 to <18 years of age who have had at least 1 PE in the prior year. Approximately 40 adolescent participants will be randomly assigned in a 2:2:1 ratio to receive brensocatib 10 mg QD, brensocatib 25 mg QD, or matching placebo QD for 52 weeks.

After baseline, participants will return to the study site for in-clinic visits at Weeks 4, 16, 28, 40, 52 (end of treatment [EOT]), and 56 (end of study [EOS]), during which they will be assessed for PEs and undergo clinical laboratory tests, vital signs measurement, and assessment by means of questionnaires (BEST, QoL-B, PGI-S/PGI-C, QoL-PCD, and EQ-5D-5L). In addition, collection of the days of work and/or school missed due to PE will occur. Telephone visits will occur at Weeks 10, 22, 34, and 46, during which collection of AEs, concomitant medications, smoking status, periodontal complaints, questionnaires (as mentioned above), and assessment for occurrence of PEs will occur. At Visit 11 (Week 52/EOT) participants will discontinue all study treatment and will be followed for a 1-month follow-up period, during which initiation of any new medical or non-medical therapy for NCFBE should be avoided.

At Visit 12 (Week 56/EOS), participants will complete all protocol-specified assessments and EOS procedures.

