#### 6.2.2. Time to (first) ICE

Time to first ICE in days will be calculated as

Time to (first) ICE (days) = start date of first ICE - date of reference + 1.

Participants who do not have an ICE during the 52-Week treatment period will be censored at time of EOT.

The date of reference will be the date of first IP administration, if not stated otherwise. If a participant was randomized but not treated with IP, the participant will be censored at study day 1 (day of randomization).

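### The uncensored by-arm median time to first periodontal referral describes only referred participants and says almost nothing about how often referral occurs

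*SAP*

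**What the plan says.** SAP 9.3 introduces its AESI outputs with "Tabulations will be prepared for each event type by treatment group". Under Periodontitis/Gingivitis, the first output is "the median time from randomization to first referral of a participant", followed by the rule "Censoring will not be applied". The other periodontal outputs listed are pocket-depth changes, dental TEAEs, gingival inflammation and severe events by SOC and PT. The number or percent of participants referred is not listed.

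Referral is a discretionary step. Protocol 9.10.3.2 says that, where signs or symptoms of periodontitis or gingivitis lead the investigator to want further evaluation, "the subject will be referred to a dentist/periodontist for further assessment and treatment". Many participants may therefore never be referred.

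SAP 9.3 also plans AESI-level summaries: "A summary of the incidence will be provided for each TEAESI by treatment group", and in addition "the risk difference estimate (unadjusted) and the exact 95% confidence interval will be provided for treatment comparison between each brensocatib dose and placebo".

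Elsewhere the SAP censors event-free participants in time-to-first-event summaries. For time to first intercurrent event, SAP 6.2.2 states "Participants who do not have an ICE during the 52-Week treatment period will be censored at time of EOT". SAP 6.7.1.6 also censors time to first PE, and SAP 8.4 has the intercurrent-event times analysed in the same way, with a plot of one minus the Kaplan-Meier estimate.

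**The concern.** Dropping censoring conditions the summary on the outcome. The median among referred participants answers the question of when a referral tended to happen, given that it happened. It does not answer how likely a participant in each arm was to be referred. The figure is nevertheless set out by arm, for an AESI category that Protocol 1.4.2 ties to DPP1 inhibition, and in a form that looks like a time-to-event comparison. Two arms with quite different referral frequencies can show nearly the same median.

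Unequal follow-up is a smaller point of the same kind. If one arm has more early withdrawal, its later referrals go unobserved, and an uncensored median can shift for that reason alone.

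What is at stake is the usefulness of one safety table. The output as written gives readers no planned comparison of referral frequency between arms.

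**Working it through.** The documents state no referral rate, expected median or power for this item, so there is no figure to reproduce. Everything below is an illustration.

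**Inputs**
- From the documents: the summary and its no-censoring rule (SAP 9.3); a 52-week treatment period and "540 participants per treatment arm" (SAP 3.1).
- Assumed: a constant referral hazard over T = 52 weeks, complete follow-up, and a share p referred by Week 52.

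**Step 1. Median among those referred.** With constant hazard λ, p = 1 − exp(−λT), so λ = −ln(1 − p)/T. Half of those referred have been referred at time t when 1 − exp(−λt) = p/2. Hence

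t = T × ln(1 − p/2) / ln(1 − p).

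- p = 2%: 52 × ln(0.99)/ln(0.98) = 52 × 0.4975 = 25.9 weeks
- p = 5%: 52 × ln(0.975)/ln(0.95) = 52 × 0.4936 = 25.7 weeks
- p = 8%: 52 × ln(0.96)/ln(0.92) = 52 × 0.4896 = 25.5 weeks
- p = 10%: 52 × ln(0.95)/ln(0.90) = 52 × 0.4868 = 25.3 weeks
- p = 20%: 52 × ln(0.90)/ln(0.80) = 24.6 weeks
- p = 40%: 52 × ln(0.80)/ln(0.60) = 22.7 weeks

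Going from 2% to 8% moves the median by 25.87 − 25.46 = 0.41 week. Doubling from 5% to 10% moves it by 0.35 week, and from 10% to 20% by 0.76 week.

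**Step 2. Size of that shift against noise.** At 540 per arm, 2% is 10.8 (about 11) participants and 8% is 43.2 (about 43). At these rates the times among those referred are close to uniform on 0 to 52 weeks. For odd n, the median of n uniform times has standard deviation 52/√(4(n + 2)). This is 52/√52 = 7.2 weeks for n = 11 and 52/√180 = 3.9 weeks for n = 43. A shift of 0.4 week is invisible against that.

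**Step 3. Simulation** (540 per arm, 5,000 runs, brensocatib arm with twice the referrals):

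| Referred, placebo vs brensocatib | Brensocatib median equal to or later than placebo | Rank-sum test on referred-only times rejects at 5% |
|---|---|---|
| 5% vs 10% | 47% of runs | 4.7% |
| 10% vs 20% | 42% of runs | 5.4% |

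The rejection rates are about what chance gives. The medians that fall on the wrong side are sampling noise and do not reflect a systematic delay.

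**Step 4. The same data with everyone counted.** At 5% versus 10%, comparing proportions has about 88% power. A log-rank test with censoring has about 90%, at a hazard ratio of ln(0.90)/ln(0.95) = 2.05. At 10% versus 20% both exceed 99%. So the information on referral frequency is in the data, and the referred-only median discards it.

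**Step 5. Would a censored median serve?** Usually not. A Kaplan-Meier median exists only if at least half the arm is referred. The useful quantities are the number and percent referred and the cumulative incidence at a fixed time.

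**The case against.** Several points on the other side are sound.

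- **The count may already appear.** SAP 6.1 says that summaries of continuous variables give the arm size N and the number of non-missing values n. Applied here, n is the number referred, and the illustration would read 11 of 540 against 43 of 540. This is an inference, because the rule is worded for scheduled visits, but it is a reasonable one. A reader might infer that the table cannot reveal more frequent referral. The documents do not support that: the limitation belongs to the median, not necessarily to the table.
- **The drug risk is assessed elsewhere in the section.** Incidence by arm, risk differences with exact intervals, dental TEAEs and severe events are all planned. A reader might infer that a periodontal signal would be hidden, or that near-equal medians would be taken as reassurance. That would require overlooking those outputs, and nothing in the documents shows it would happen. What remains is that AESIs are identified from the category the investigator selects on the AE form, whereas referral can follow any signs or symptoms judged to need evaluation. One does not replace the other.
- **Referral is a process measure.** It depends on investigator discretion, and no objective or estimand uses it. This limits the importance of the point.
- **The intended denominator is unclear.** The dedicated eCRF forms are not in the documents. If referral dates are recorded only for AESI cases, the median describes those cases and their frequency is already given by the AESI incidence.
- **The near-equal medians follow from the assumed timing.** If the drug brought referrals forward or delayed them, the median would move. As a descriptor of timing among those referred, it is legitimate.

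**Conclusion.** The point holds as a minor one. The no-censoring rule is explicit. It follows, although the SAP does not spell it out, that only referred participants contribute to the median. Under a constant hazard, that median changes by about 0.4 week between 2% and 8% referred, well inside sampling noise at 540 per arm. The referral rates and the constant hazard are assumptions. The general argument needs only that the timing of referrals is similar in the arms.

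The scope is one descriptive safety summary. A reader might go further and infer that a higher-risk arm would tend to show a later median. The calculation does not support this: under constant hazards the higher-risk arm's true median is slightly earlier, and later values arise only by chance. The AESI analysis as a whole is not undermined, and no efficacy conclusion or type I error is involved.

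**What to change.** In SAP 9.3, under Periodontitis/Gingivitis:

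1. Report by arm the number and percent of participants with a first periodontal referral, and state the denominator.
2. Add the Kaplan-Meier cumulative incidence of first referral at Week 52 by arm, with unreferred participants censored at end of follow-up. The PROC LIFETEST set-up in SAP Appendix I for time to first PE can be reused.
3. If the uncensored median is kept, label it as calculated among referred participants.

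Provided that referral dates are collected for everyone referred, this needs no new data. The cost is a change of SAP wording and one additional descriptive table. If the eCRF records referral only for AESI cases, the SAP should say so, and items 1 and 3 are then enough.
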